10.1.9.2. Study/Site Termination

The sponsor or designee reserves the right to close the study site or terminate the study at any time for any reason at the sole discretion of the sponsor. Study sites will be closed upon study completion. A study site is considered closed when all required documents and study supplies have been collected and a study site closure visit has been performed.

Administration of the study agent will be temporarily suspended by the SMT upon the occurrence of any of the following:

- Unexpected SAEs within the same SOC or similar in nature are reported by 2 or more participants on active study intervention with a plausible relationship to study intervention administration.
- 1 or more participants on active study intervention meets Hy's Law Criteria as defined in [Appendix 7](#).

Based on the sponsor review and evaluation of the aforementioned safety events, the study may be restarted or terminated.

The investigator may initiate study site closure at any time, provided there is reasonable cause and sufficient notice is given in advance of the intended termination.

Reasons for the early closure of a study site by the sponsor or investigator may include but are not limited to:

For study termination:

- Sponsor makes a business decision to stop the study.
- Study stopping criteria are met and following investigation, the sponsor decides to stop the study.
- Ongoing evaluation of study safety data suggests that the benefit-risk profile suggests stopping the study.

For site termination:

- Failure of the investigator to comply with the protocol, the requirements of the IRB/IEC or local health authorities, the sponsor's procedures, or GCP guidelines
- Inadequate or no recruitment (evaluated after a reasonable amount of time) of participants by the investigator
- Total number of participants included earlier than expected

If the study is prematurely terminated or suspended, the sponsor shall promptly inform the investigators, the IECs/IRBs, the regulatory authorities, and any contract research organization(s) used in the study of the reason for termination or suspension, as specified by the applicable regulatory requirements. The investigator shall promptly inform the participant and should assure appropriate participant therapy and/or follow-up.

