APPENDIX 7. LIVER SAFETY: SUGGESTED ACTIONS AND FOLLOW-UP ASSESSMENTS

Table 7: Phase 2 Liver Chemistry Stopping Criteria and Follow-up Assessments

Liver Chemistry Stopping Criteria	
ALT-absolute	ALT $\geq 5 \times$ ULN
ALT Increase	ALT $\geq 3 \times$ ULN persists for ≥ 4 weeks
Total bilirubin^{a,b}	ALT $\geq 3 \times$ ULN and total bilirubin $\geq 2 \times$ ULN ($> 35\%$ direct bilirubin)
INR^b	ALT $\geq 3 \times$ ULN and INR > 1.5 , if INR measured
Cannot Monitor	ALT $\geq 3 \times$ ULN and cannot be monitored weekly for 4 weeks
Symptomatic^c	ALT $\geq 3 \times$ ULN associated with symptoms (new or worsening) believed to be related to liver injury or hypersensitivity
Suggested Actions, Monitoring and Follow-up Assessments	
Actions	Follow-up Assessments

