
Immediately discontinue study intervention.
 
Record the Liver Stopping Events as an AE, and report to the sponsor or designee as an ORE, as described in Appendix 4.
 
If the Liver Stopping Event also meets the criteria for an SAE, record and report to the sponsor or designee as an SAE, as described in Appendix 4.
 
Perform follow-up assessments as described in the Follow-Up Assessment column.
 
Monitor the participant until liver chemistry test abnormalities resolve, stabilize, or return to baseline (see MONITORING).
 
MONITORING:
 
If ALT $\geq 3 \times$ ULN AND total bilirubin $\geq 2 \times$ ULN or INR > 1.5:
 
Repeat liver chemistry tests (include ALT, AST, alkaline phosphatase, total bilirubin and INR) and perform liver event follow-up assessments within 24 hours.
 
Monitor participant twice weekly until liver chemistry test abnormalities resolve, stabilize, or return to baseline.
	
Viral hepatitis serology.^d
 
Obtain INR and recheck with each liver chemistry assessment until the transaminases values show downward trend.
 
Obtain blood sample for PK analysis.^e
 
Obtain serum creatine phosphokinase, lactate dehydrogenase, GGT, glutamate dehydrogenase, and serum albumin.
 
Fractionate bilirubin, if total bilirubin $\geq 2 \times$ ULN.
 
Obtain complete blood count with differential to assess eosinophilia
 
Record the appearance or worsening of clinical symptoms of liver injury, or hypersensitivity as an AE.
 
Record use of concomitant medications (including acetaminophen, herbal remedies, recreational drugs and other over-the-counter medications) and provide information via email to [contact].
 
If ALT $\geq 3 \times$ ULN AND total bilirubin $< 2 \times$ ULN or INR > 1.5 obtain the following in addition to the assessments listed above:
 
Anti-nuclear antibody, anti-smooth muscle antibody, Type 1 anti-liver kidney microsomal antibodies, and quantitative total immunoglobulin G or gamma globulins.

Liver Chemistry Stopping Criteria	

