
A specialist or hepatology consultation is recommended.
 
If $ALT \geq 3 \times ULN$ AND total bilirubin $< 2 \times ULN$ and INR ≤ 1.5:
 
Repeat liver chemistry tests (include ALT, AST, alkaline phosphatase, total bilirubin and INR) and perform liver chemistry follow-up assessments within 24 to 72 hours.
 
Monitor participants weekly until liver chemistry abnormalities resolve, stabilize, or return to baseline.
 
Permanently discontinue study intervention and continue participant in the study for any protocol-specified follow-up assessments.
	
Serum acetaminophen adduct assay, when available, to assess potential acetaminophen contribution to liver injury in participants with definite or likely acetaminophen use in the preceding week.
 
Liver imaging (ultrasound, magnetic resonance, or computerized tomography) and/or liver biopsy to evaluate liver disease. Provide liver imagine results via email to [contact].
 
Liver biopsy may be considered and discussed with local specialist if available:
 
In participants when serology raises the possibility of autoimmune hepatitis.
 
In participants when suspected drug-induced liver injury progresses or fails to resolve on withdrawal of study intervention.
 
In participants with acute or chronic atypical presentation
 
If liver biopsy conducted, provide liver imaging results via email to [contact].

^a Serum bilirubin fractionation should be performed if testing is available. If serum bilirubin fractionation is not immediately available, discontinue study intervention if $ALT \geq 3 \times ULN$ and total bilirubin $\geq 2 \times ULN$.

Additionally, if serum bilirubin fractionation testing is unavailable, **record the absence/presence of detectable urinary bilirubin on dipstick which** is indicative of direct bilirubin elevations suggesting liver injury.

^b All events of $ALT \geq 3 \times ULN$ and total bilirubin $\geq 2 \times ULN$ ($> 35\%$ direct bilirubin) or $ALT \geq 3 \times ULN$ and INR > 1.5 may indicate severe liver injury (**possible “Hy’s Law”**) and **must be reported to sponsor in an expedited manner and as an SAE if SAE criteria met**. The INR stated threshold value will not apply to participants receiving anticoagulants.

^c New or worsening symptoms believed to be related to liver injury (such as fatigue, nausea, vomiting, right upper quadrant pain or tenderness, or jaundice) or hypersensitivity (such as fever, rash or eosinophilia).

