^d Includes: Hepatitis A immunoglobulin M (IgM) antibody; hepatitis B virus surface antigen (HBsAg) and hepatitis B core antibody (HBcAb); hepatitis C RNA; cytomegalovirus IgM antibody; Epstein-Barr viral capsid antigen IgM antibody (or if unavailable, heterophile antibody or monospot testing); and hepatitis E IgM antibody.

^e PK sample may not be required for participants known to be receiving placebo. Record the date/time of the PK blood sample draw and the date/time of the last dose of study intervention prior to the blood sample draw on the CRF. If the date or time of the last dose is unclear, provide the participant’s best approximation. If the date/time of the last dose cannot be approximated OR a PK sample cannot be collected in the time period indicated above, do not obtain a PK sample. Instructions for sample handling and shipping are in the Investigator Trial Site Binder.

Table 8: Phase 2 Liver Chemistry Increased Monitoring Criteria with Continued Study Intervention

Liver Chemistry Increased Monitoring Criterion and Actions With Continued Study Intervention	
Criterion	Actions
ALT $\geq 3 \times$ ULN and $< 5 \times$ ULN and total bilirubin $< 2 \times$ ULN or INR < 1.5 , without symptoms believed to be related to liver injury or hypersensitivity, and who can be monitored weekly for 4 weeks	Notify the sponsor within 24 hours of learning of the abnormality to discuss participant safety. Participant can continue study intervention. Participant must return weekly for repeat liver chemistry tests (ALT, AST, alkaline phosphatase, total bilirubin) until the abnormalities resolve, stabilize or return to baseline. If at any time, the participant meets liver chemistry stopping criteria, proceed as described in Section 7.1 . If, after 4 weeks of monitoring, ALT $< 3 \times$ ULN and total bilirubin $< 2 \times$ ULN, monitor participants twice monthly until liver chemistry tests resolve, stabilize, or return to baseline.

Signature Page for JZP150-201-02 Protocol Amendment - Published (VV-CLIN-013888)

Approval Task - Approval of Document Signing Verdict/Reason: I Approved This Document	
	16-Nov-2022 18:05:52 GMT+0000

Signature Page for JZP150-201-02 Protocol Amendment - Published (VV-CLIN-013888)

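### Protocol Table 8 requires no INR while dosing continues at ALT 3 to < 5 x ULN, so the INR-based liver safeguards can be delayed or missed

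*Protocol*

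**What the plan says.** **Table 8 (continued dosing).** Entry needs ALT 3 to < 5 x ULN, no symptoms attributed to liver injury or hypersensitivity, feasible weekly monitoring for 4 weeks, and "total bilirubin $< 2 \times$ ULN or INR < 1.5". The weekly requirement is: "Participant must return weekly for repeat liver chemistry tests (ALT, AST, alkaline phosphatase, total bilirubin) until the abnormalities resolve". The sponsor must be told within 24 hours, and the Table 7 stopping criteria apply throughout. The step-down after 4 weeks uses ALT and total bilirubin only.

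**Table 7 (stopping).** One row stops drug at ALT >= 3 x ULN with INR > 1.5, qualified by "if INR measured". Once any stopping row is met and drug is withdrawn, INR is compulsory: "Obtain INR and recheck with each liver chemistry assessment until the transaminases values show downward trend". Both monitoring branches of that table also name it: "Repeat liver chemistry tests (include ALT, AST, alkaline phosphatase, total bilirubin and INR". Footnote b treats ALT >= 3 x ULN with INR > 1.5 as possible Hy's Law, and adds: "The INR stated threshold value will not apply to participants receiving anticoagulants".

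**Routine laboratory panel.** The visible part of Table 6 (Appendix 3) lists no INR. Its footnote b gives the same INR limb, for ALT or AST, again only where INR has been measured.

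**Trial level.** Protocol 10.1.9.2 temporarily suspends dosing when "1 or more participants on active study intervention meets Hy's Law Criteria as defined in" Appendix 7.

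**The concern.** Table 8 covers people who have raised ALT and are still taking the drug. One criterion for stopping them, and one limb of possible Hy's Law, turn on INR. Yet nothing visible obliges a site to draw INR at that stage. A participant with ALT 3 to < 5 x ULN, bilirubin below 2 x ULN and an INR above 1.5 that nobody has measured would look like an ordinary Table 8 case and could go on dosing.

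More than one participant is affected. A single Hy's Law case on active drug is meant to pause dosing across the trial, so late recognition through INR also delays protection for everyone else.

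**Working it through.** No power, alpha or event figure bears on this point, so the check compares the tables and counts required tests.

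**Step 1. Where is INR required?**

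| Place | Dosing status | INR required? |
|---|---|---|
| Table 6, routine panel (visible entries) | on drug | no |
| Table 8, weekly repeats | on drug | no (4 analytes) |
| Table 7, repeat panels, both branches | drug stopped | yes (5 analytes, including INR) |
| Table 7, follow-up list | drug stopped | yes |
| SAP Appendix 3, panic values | not applicable | no; a standard laboratory chart with an INR limit of 5.0 |

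Table 7's weekly-monitoring branch (ALT >= 3 x ULN, bilirubin < 2 x ULN, INR <= 1.5) overlaps the liver state in Table 8. The panel with INR goes to people already off drug, and the panel without it to people still exposed.

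**Step 2. Can a participant enter Table 8 with no INR?** Yes. The criterion joins bilirubin and INR by *or*, so bilirubin < 2 x ULN is enough by itself.

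**Step 3. Which rules need an INR result?**

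- The Table 7 INR stopping row.
- The INR limb of possible Hy's Law (Table 6 footnote b, Table 7 footnote b), with its expedited reporting.
- The suspension rule in Protocol 10.1.9.2, so far as it works through that limb.

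**Step 4. How long is the window?** ALT >= 3 x ULN lasting >= 4 weeks is itself a stopping criterion, so continued dosing at this ALT level is limited to about 4 weeks.

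- Weekly visits in the window: 4 weeks x 1 per week = 4.
- Required INR tests now: 4 x 0 = 0.
- Required INR tests with INR in the weekly panel: 4 x 1 = 4 at most, fewer if ALT settles sooner.

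If ALT stays at this level, the first compulsory INR follows the persistence stop, about 4 weeks after detection. With the change it comes at the first weekly repeat. If ALT falls below 3 x ULN with no other stop, INR is never required under the present text.

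**Step 5. Does the *or* wording create a conflict once INR is known?** No. Bilirubin < 2 x ULN with a measured INR > 1.5 satisfies both the Table 8 criterion and the Table 7 stop, but Table 8 makes the stopping criteria prevail and Protocol 7.1.1 makes discontinuation compulsory. The weakness is the missing test.

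**The case against.** The strongest reply is that INR was made conditional on purpose. The stopping row carries the words "if INR measured", so INR is an optional extra trigger and its absence breaks no rule. Much of this stands. A reader might infer that a participant with an unmeasured high INR already meets a stopping criterion and is dosed in breach of it. The text does not support that, because without a result the row is not met. This is a gap in required testing, not a contradiction.

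A reader might also infer that the suspension rule cannot operate through INR. That is too strong. Appendix 3 allows the investigator to add tests at any time, and Table 7 requires INR after every stop. The INR route can be delayed or missed, but it is not closed.

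Several other safeguards also remain:

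- stops for ALT >= 5 x ULN, for bilirubin, for symptoms, for inability to monitor, and for 4-week persistence;
- sponsor notification within 24 hours under Table 8;
- reporting of elevated liver tests as other reportable experiences within 24 hours (Appendix 4);
- monthly hepatic review by the internal safety committee, with an ad hoc safety management team that can unblind and act (Protocol 10.1.5);
- investigator discretion to stop (Protocol 7.1.1).

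None of these requires INR before drug is stopped, but together they make the gap narrow.

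Redaction is a further limit. One Table 6 entry is partly blacked out, and laboratory categories are hidden elsewhere, so the absence of INR from routine testing is likely but not fully verifiable.

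The reply does not explain why INR is left out of a monitoring table that uses INR as its own criterion, at visits that are already compulsory.

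**Conclusion.** The omission is real, and the change is a cheap improvement to consider. In the visible protocol no INR is required during up to about 4 weeks of continued dosing at ALT 3 to < 5 x ULN, while the INR stop and the INR limb of possible Hy's Law depend on that result.

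The documents give no frequency for this state. Protocol 2.2 reports no laboratory safety concerns in earlier sponsor studies, so it is probably rare, although Protocol 4.3 describes 4 mg daily in patients for only up to 30 days against 12 weeks here. The benefit cannot be quantified. Avoided doses are not a fair measure of it, since such a count would assume that INR is raised from the outset, that no other stop is met, and that nobody orders INR after the sponsor is called. The conclusion rests on the redacted laboratory entries not containing INR. Confidence is high in the omission and modest in its practical effect.

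**What to change.** 1. Add INR to the Table 8 weekly repeat list, starting at the first repeat visit after ALT >= 3 x ULN is known. It need not join the routine panel.
2. Reword that part of the criterion as: total bilirubin < 2 x ULN and INR <= 1.5 (once measured).
3. Keep the anticoagulant exception in footnote b and the bilirubin fractionation rule in footnote a of Table 7.

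**Cost.** Amendment wording, plus up to about 4 INR assays per affected participant at visits already required; Protocol Section 8 already allows unscheduled safety samples. The documents give no ALT rate. If 1% to 3% of the 270 participants entered Table 8 (an assumption), that is 270 x 0.01 = 2.7 to 270 x 0.03 = 8.1 participants, and at most 2.7 x 4 = 10.8 to 8.1 x 4 = 32.4 assays, or about 11 to 32. There may be a few more discontinuations, or a temporary suspension, under rules that already exist. With *and* in place of *or*, a participant whose bilirubin is >= 2 x ULN but mostly indirect no longer enters Table 8 on INR alone, and is left to investigator judgement under Protocol 7.1.1.

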1. LIST OF ABBREVIATIONS

Abbreviation	Definition
AE	Adverse event
AEA	Anandamide
ALQ	Above the Limit of Quantification
ALT	Alanine aminotransferase
ANCOVA	Analysis of Covariance
APTT	Activated partial thromboplastin time
AST	Aspartate aminotransferase
ATC	Anatomical therapeutic class
AUC	Area under the plasma concentration-time curve
B-IPF	Brief Inventory of Psychosocial Functioning
BLQ	Below the Limit of Quantification
BMI	Body mass index
CAPS-5	Clinician Administered PTSD Scale for DSM-5
CAPS-5 Total Score	Clinician Administered PTSD Scale total symptom severity score
CDISC	Clinical Data Interchange Standards Consortium
CGI-C	Clinical Global Impression of Change
CGI-S	Clinical Global Impression of Severity
CI	Confidence Interval
CK	Creatine kinase
cm	Centimeter
C _{max}	Maximum plasma concentration
CMH	Cochran-Mantel-Haenszel
CNR1	Cannabinoid receptor type 1
COVID-19	Coronavirus disease 2019
CSR	Clinical Study Report
C-SSRS	Columbia Suicide Severity Rating Scale
CTMS	Clinical Trial Management System
CV	Coefficient of variation
DBP	Diastolic blood pressure
DSM-5	Diagnostic and Statistical Manual of Mental Disorders, 5 th Edition
ECG	Electrocardiogram
EDC	Electronic data capture
eCRF	Electronic case report form

Jazz Pharmaceuticals
 {Statistical Analysis Plan - Protocol #}JZP150-201-02

E/D	Early discontinuation
EoS	End of study
F	Female
FAAH	Fatty acid amide hydrolase
HCG	Human chorionic gonadotropin
HGB	Hemoglobin
HR	Heart rate
ICE	Intercurrent event
ICF	Informed consent form
ICH	International Council for Harmonization
INR	International normalized ratio
ILS	ICON Laboratory Services
IRT	Interactive response technology
ISI	Insomnia Severity Index
ITT	Intention-to-Treat
kg	Kilogram
kg/m ²	Kilogram per square meter
LEC-5	Life Event Checklist for DSM-5
LLN	Lower limit of normal
LS	Least square
M	Male
MAR	Missing at random
Max	Maximum
MedDRA	Medical Dictionary for Regulatory Activities
Min	Minimum
min	Minute
MINI	Mini International Neuropsychiatric Interview
mmHg	Millimeter of mercury
MMRM	Mixed-effect model with repeated measures
MNAR	Missing not at random
msec	Millisecond
MWC	Marijuana withdrawal checklist
n	Number of participants
PCL-5	PTSD Checklist for DSM-5
PD	Pharmacodynamics

Jazz Pharmaceuticals
 {Statistical Analysis Plan - Protocol #}JZP150-201-02

PE	Physical examination
PG	Pharmacogenomics
PGI-S	Patient Global Impression of Severity
PHQ-9	Patient Health Questionnaire-9
PK	Pharmacokinetics
PSQI	Pittsburgh Sleep Quality Index
PSQI-A	Pittsburgh Sleep Quality Index - PTSD Addendum
PT	Preferred Term
PT	Prothrombin time
PTSD	Posttraumatic Stress Disorder
QD	Once daily
QTcB	QT Bazett's Correction
QTcF	QT Fridericia's Correction
REML	Restricted maximum likelihood estimation
ReQoL	Recovering Quality of Life
SAE	Serious adverse event
SAP	Statistical analysis plan
SD	Standard deviation
SE	Standard error
SBP	Systolic blood pressure
SDS	Sheehan Disability Scale
SIGH-A	Structured Interview Guide for the Hamilton Anxiety Rating Scale
SNRI	Serotonin norepinephrine reuptake inhibitor
SOC	System Organ Class
SSRI	Selective serotonin reuptake inhibitor
$t_{1/2}$	Terminal half-life
TEAE	Treatment emergent adverse event
T_{max}	Time to maximum concentration
ULN	Upper limit of normal
yrs	Years
WBC	White blood cell
WHO	World Health Organization

Jazz Pharmaceuticals
{Statistical Analysis Plan - Protocol #}JZP150-201-02

2. MODIFICATION HISTORY

Version History for SAP:

Version	Date	Description
Version 1.0	12 Dec 2023	Original

Jazz Pharmaceuticals
{Statistical Analysis Plan - Protocol #}JZP150-201-02

3. INTRODUCTION

The purpose of this statistical analysis plan (SAP) is to describe in detail the statistical methodology and planned analyses to be conducted for Protocol JZP150-201-02 for inclusion in the Clinical Study Report (CSR). The current version is based on Protocol Amendment 02 dated 16 November 2022. Any additional analyses or deviation from the analyses outlined in this plan will be documented with rationale in SAP amendments and in the final CSR.

Jazz Pharmaceuticals
{Statistical Analysis Plan - Protocol #}JZP150-201-02

4. STUDY OBJECTIVES AND ENDPOINTS

4.1. Study Objectives

4.1.1. Primary Objective

To evaluate the efficacy of JZP150 administered once daily for up to 12 weeks at doses of 0.3 mg and 4 mg compared to placebo in the treatment of adults with posttraumatic stress disorder (PTSD), as measured by the change in Clinician Administered PTSD Scale for DSM-5 (CAPS-5) total symptom severity score (CAPS-5 total score).

4.1.2. Key Secondary Objective

To evaluate the efficacy of JZP150 administered once daily for 12 weeks at doses of 0.3 mg and 4 mg compared to placebo on overall clinician and patient impression of severity.

4.1.3. Secondary Objectives

The secondary objectives of the study are:

- To evaluate the efficacy of JZP150 administered once daily for 12 weeks at doses of 0.3 mg and 4 mg compared to placebo on functional outcomes and participant reported symptoms in adults with PTSD.
- To evaluate the safety and tolerability of JZP150 administered once daily for up to 12 weeks at doses of 0.3 mg and 4 mg in adults with PTSD.
- To characterize the pharmacokinetic (PK) and pharmacodynamics (PD) of JZP150 in adults with PTSD using population PK modeling and simulation methodology.

4.2. Study Estimands and Endpoints

Study estimands and intercurrent events (ICEs) strategies are constructed based on International Conference on Harmonization (ICH) E9 (R1) ([ICH 2021](#)).

4.2.1. Primary Estimand

The primary estimand of the study is defined as:

- Treatment: 0.3 mg and 4 mg of JZP150, and placebo.
- Population: Participants with PTSD (as defined in the eligibility criteria).
- Variable (endpoint): CAPS-5 total score change from Baseline to Week 12.
- ICEs: The main ICE treatment discontinuation will be addressed by treatment policy (primary strategy) and hypothetical approach (alternative strategy). Other possible ICEs are defined in [Section 7.6](#).

Jazz Pharmaceuticals
{Statistical Analysis Plan - Protocol #}JZP150-201-02

- Population-level summary: The mean change from Baseline to Week 12 in CAPS-5 total score for each randomized treatment group and the difference in means between each randomized treatment group compared to placebo.

